#### MOAAS:

- 0 No response after painful trapezius squeeze
- 1 Responds only after painful trapezius squeeze
- 2 Responds only after mild prodding or shaking
- 3 Responds only after name is called loudly and/or repeatedly
- 4 Lethargic response to name spoken in normal tone
- 5 Responds to name spoken in normal tone

### 5.4 Crossover to Other Group After Randomization

Patients in either Group A or Group B will be eligible for crossover to the other group at the discretion of the anesthesiologist in order to safely complete the procedure and minimize the likelihood of future adverse events.

Group A (Standard care with a nasal cannula) to Group B (SuperNO2VA™EtCO2) group will occur when during the procedure either: 1) twoor more simultaneous or non-synchronous adverse events related to changes in SBP, SpO2 or HR that do not respond to typical maneuvers to reverse these or; 2) any of the following two occur: a) any change in heart rhythm other than sinus bradycardia or sinus tachycardia or; b) ST changes appear on EKG occur.

Group B to Group A: If any of the following occur: 1) patient refusal to wear the mask once placed due to claustrophobia, poor fit or discomfort or any other reason; 2) two or more simultaneous or non-synchronous adverse events related to changes in SBP, Sp02 or HR that do not respond to typical maneuvers to reverse these or; 3) any of the following two occur: a) any change in heart rhythm other than sinus bradycardia or sinus tachycardia or; b) ST changes appear on EKG occur.

## 6. SUBJECT WITHDRAWALS

Subjects may be withdrawn from the study for the following reasons:

- 1. Unacceptable adverse events (safety or tolerability)
- 2. The subject's may withdraw from the study at any time and for any reason
- 3. Clinician decision that it is in the best interest of the subject to withdraw from the study

### 7. SAFETY AND REPORTABLE EVENTS

### 7.1. Adverse Event Definition

Adverse Event (AE): An Adverse Event is any undesirable clinical event occurring to the subject during clinical study, whether or not it is considered related to the investigational product. This includes a change in a subject's condition or laboratory results, which has or could have a deleterious effect on the subject's health or well-being. An Adverse Event that is related to the investigational device may be referred to as an Adverse Device Effect (ADE).

### **Adverse Events**

For study conduct purposes, adverse events will be categorized at the investigative site into two groups: Serious Adverse Events, and Non-Serious Adverse Events. The Investigator as either related to the device or its deployment, or not related to the device or its deployment will assess the causal relationship of each adverse event. Each Adverse Event assessed as being related to the device or its deployment will also be assessed by the Investigator as being anticipated or unanticipated.

### An adverse event does not include:

- Medical or surgical procedures; the condition that leads to the procedure is not an adverse event
- Pre-existing disease, conditions, or laboratory abnormalities present at the start of the study that do not worsen in frequency or intensity
- Situations where an untoward medical occurrence has not occurred (e.g., hospitalizations for cosmetic or elective surgery or social/convenience admissions)
- Expected ICU course

Protocol #: IU IRB# 1810997768 Date: 31AUG21 Page 11 of 17

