# 1. OBJECTIVES

# **Primary Objective**

The primary objective of the study is to prospectively and randomly compare the incidence, duration, and severity of oxygen desaturation between a nasal mask with nasal positive airway pressure (PAP) versus standard care (nasal cannula) during propofol-based sedation for endoscopic ultrasound in an ambulatory surgical center (ASC) in patients considered high risk for hypoxia (ie: BMI ≥35 kg/m^2 or documented Obstructive Sleep Apnea.

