#### b) Exclusion Criteria:

- 1. Inpatient status
- 2. Active Congestive Heart Failure Exacerbation
- 3. Untreated ischemic heart disease
- 4. Acute exacerbation of respiratory disorders, including COPD and asthma
- 5. Emergent procedures
- 6. Pregnancy
- 7. Previous enrollment in this study
- 8. Inability to provide informed consent
- 9. Additional medical testing planned for the same day
- 10. History of allergic reaction to Propofol
- 11. Tracheostomy
- 12. Supra-glottic or sub-glottic tumor
- 13. Gastrointestinal tract obstruction or delayed transit (including delayed gastric emptying, gastric bezoar, achalasia, toxic megacolon).

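### The adverse event definition excludes any condition that leads to a procedure, so a new harm that needs a procedure can miss the AE and SAE records

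*Protocol*

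**What the plan says.** Protocol section 7.1 opens with a wide definition: "An Adverse Event is any undesirable clinical event occurring to the subject during clinical study, whether or not it is considered related" (that is, related to the study device). Under the subheading Adverse Events it adds that "adverse events will be categorized at the investigative site into two groups: Serious Adverse Events, and Non-Serious Adverse Events".

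A list of what an AE does not include follows. Three of its four items matter here:

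- The first item, on procedures, reads "Medical or surgical procedures; the condition that leads to the procedure is not an adverse event".
- The second item, on conditions already there at entry, reads "Pre-existing disease, conditions, or laboratory abnormalities present at the start of the study that do not worsen in frequency or intensity".
- The last item, on intensive care, reads "Expected ICU course".

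The remaining item covers situations in which nothing untoward happened, such as elective or social admissions. The protocol does not define the ICU item or mention an ICU anywhere else. The SAP has no AE definition of its own. Its section 1.3 repeats the halfway AE tabulation of protocol section 10.3 and so relies on the protocol's definition.

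**The concern.** The first item excludes two different things: the procedure, and the condition that made it necessary. Excluding the procedure is sensible, since an intervention is not itself a harm. Excluding the condition is not, because the condition is what a safety record should capture. The effect is perverse: a corneal injury left alone is an AE, while the same injury treated by a procedure is not.

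The accuracy of the AE and serious AE (SAE) record for a device trial is at stake. Staff who follow the list literally would leave out new harms because they needed a procedure, and those responsible for safety would not see them through the AE route.

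The ICU item is a lesser problem. It has no meaning in this trial, and it leaves staff to decide what an expected ICU course might be.

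**Working it through.** No arithmetic applies. The check has three parts: whether the bullet has a harmless reading, which records depend on it, and what those records would miss.

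**1. Is there a harmless reading?** The natural one is that the bullet means only the indication for the index endoscopic ultrasound. The text does not say so. That indication is present at entry, and the next bullet already deals with conditions present at the start, on the condition that they do not worsen. The first bullet has neither limit: it does not mention entry, worsening or the study procedure. On its wording it reaches conditions that arise during or after sedation, which the opening definition includes. The two statements in section 7.1 conflict.

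**2. Which records depend on the AE definition?** SAEs are one of two categories into which AEs are sorted, so an event that is not an AE cannot be an SAE. It follows that these are exposed:

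- the Adverse Event Form, and AE reporting to the IRB (section 7.3);
- adverse device effects, defined in section 7.1 as device-related AEs, and the first part of the unanticipated adverse device effect (UADE) definition in section 7.2;
- the AE tabulation for the halfway DSMB meeting (protocol 10.3, SAP 1.3);
- the outside reviewers' review of AEs and their 24-hour review of SAEs (section 12, Data Safety Monitoring).

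These are not exposed, because they are counted under their own definitions (Summary Table; sections 5.2 and 5.3):

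- oxygen desaturation, the primary outcome;
- cardiac complications;
- airway maneuvers, including supraglottic device and endotracheal tube insertion, with the reason recorded;
- procedural interruptions for a respiratory complication;
- the second part of the UADE definition, which covers other unanticipated serious device problems and does not require an AE.

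One item is unclear. Section 7.3 tells the principal investigator to record all serious adverse experiences, a term it does not define, in source documents and/or the AE log. That points towards capture, but it does not ensure that the event is tabulated or sent to the outside reviewers.

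**3. What is left uncovered?** Subtracting the second list from the first leaves harms that no endpoint records as such:

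- *Aspiration.* Its consequences might register as desaturation, but the event itself is not an endpoint.
- *Anaphylaxis, ocular injury and pressure ulcer.* Section 8.1 names these as recognised risks of the mask. A hemodynamic effect of anaphylaxis might count as a cardiac complication; the other two have no endpoint at all. Because they are already recognised, they may not qualify as unanticipated, so the UADE route can miss them too.

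For these harms the AE form is the main way into the safety record, and the first bullet closes it when the harm leads to a procedure.

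**The ICU bullet.** Section 3.2 b excludes "Inpatient status" and emergent procedures, and section 1 places the trial in an ambulatory surgical center. No ICU stay is planned, and the separate item on elective and social admissions already covers planned hospital stays. The bullet therefore has no use here.

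**The case against.** The strongest reply is that little is lost. The main respiratory and cardiac harms of sedation are endpoints, the halfway review looks at the primary endpoints as well as AEs, unanticipated serious device problems are reportable under section 7.2, and section 7.3 asks for all serious adverse experiences. Section 5.4 itself calls changes in blood pressure, saturation and heart rate adverse events, so the authors plainly did not mean to hide such cases.

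Much of this stands, and it rules out three stronger readings:

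- *That the gravest harms vanish from every safety count.* They do not. A patient who is intubated is still counted under airway maneuvers, with the reason. What could be missing is the SAE classification of the underlying respiratory failure, and with it the 24-hour review.
- *That the ICU bullet hides ICU admissions.* It removes only an expected course. In outpatients with no planned ICU care, no stay is expected, so on a fair reading the bullet removes nothing. It is undefined and out of place, which is reason enough to delete it.
- *That the number of lost events, or its effect on a confidence limit, can be estimated.* Neither document gives a rate for harms that lead to a procedure, and neither plans confidence limits for AE rates. Any figure would rest on an assumed rate alone.

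The reply does not remove the contradiction within section 7.1, and it does not cover the mask harms in section 8.1. Intent is no safeguard when the written rule says the opposite.

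**Conclusion.** The point holds as a contradiction in a reporting definition. Following the first bullet as written would misclassify a new or worsened condition that leads to a procedure as neither an AE nor an SAE. The effect is confined to the AE-based records and reviews. The primary outcome, its analysis and the halfway efficacy assessment do not use the AE definition. Within the safety record, the gap that remains is harms not captured by an endpoint, chiefly aspiration and the listed mask harms, when they need a procedure.

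The size cannot be stated as a number from these documents. The conclusion rests on a literal reading of the bullet. A reader might infer that events have already been lost; the documents do not show whether site staff applied the bullet that way. The wording should still be corrected, because the list is the rule that staff are given and the correction costs little.

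**What to change.** Reconcile the opening definition in section 7.1, its list of exclusions, and section 7.3:

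1. Reword the first bullet along these lines: *Medical or surgical procedures themselves, and the indication for the index endoscopic ultrasound. A condition that arises or worsens after randomisation and leads to a procedure is an adverse event.*
2. Delete the ICU bullet, and state that an unplanned ICU or hospital transfer is recorded as an AE.
3. In section 7.3, either define serious adverse experiences or replace the term with serious adverse events, so that one definition governs the form, the log, the tabulation and the outside review.
4. If patients have already been enrolled, check their records for events left out under the current bullet, and add any that are found.

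The cost is a short amendment, a few more AE forms, a record check if enrolment has begun, and possibly slightly higher reported AE rates. No endpoint, sample size or treatment procedure changes.

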## 7.2. Unanticipated Adverse Device Effect (UADE)

Any device related adverse event, the nature or severity of which is not consistent with or listed in the applicable product information (e.g., instructions for use, subject informed consent document, subject information brochure [if applicable], promotional literature) or any other unanticipated serious problem associated with a device that relates to the rights, safety, or welfare of subjects.

### 7.3. Responsibilities for Reporting Serious Adverse Events

All adverse events, whether observed by the Investigator, elicited from or volunteered by the subject, should be documented. Each adverse event will include a brief description of the experience, the date of onset, the date of resolution, the duration and type of experience, the severity, the relationship to investigational product (i.e., drug or device), contributing factors, and any action taken with respect to the study drug/device.

Investigators and research coordinators will be instructed that all AE and corresponding relevant information should be recorded on the Adverse Event Form. In addition, the clinical site will be responsible for notifying Sponsor within 24 hours of any UADE. All relevant information regarding an UADE should be recorded on the Adverse Event Form and reported to Sponsor via Fax within 24 hours of the event. In addition to the event form, copies of adverse device effect related source documents should be forwarded to the Sponsor.

The Principal Investigator is responsible for reporting AEs to the IRB of record in accordance with IRB procedures. The Sponsor is responsible for informing the appropriate regulatory authorities and other Investigators of any UADEs that have occurred.

The Principal Investigator will record all serious adverse experiences that occur during the study period in the appropriate source documents and/or AE log as applicable.

### 8. RISK/BENEFIT ASSESSMENT

### 8.1. Potential Risks

As with use of all medical devices, complications may occur. Recognized risks associated with the use of the study intervention include, but are not limited to, the following:

- Allergic reactions: although the materials being used are hypoallergenic and the risk is small, there remains a risk for an allergic reaction that may result in hives, swelling, or anaphylaxis.
- Ocular injury: although the SuperNO2VA Et™ Mask was designed to contour away from the eyes, mishandling of the mask or accidental slippage from its intended position may result in contact with the subject's eye, resulting in a corneal abrasion and/or other ocular injury.
- Pressure ulcer: although the clinical protocols states to remove the SuperNO2VA Et™ after successful placement of an invasive airway, if the SuperNO2VA Et™ is mistakenly left on the subject for an extended period of time it can lead to a pressure ulcer.

### 8.2. Risks Minimization

- To minimize the risk of allergic reactions the SuperNO2VA Et™ has undergone and successfully passed biocompatibility testing. However, there is still a very small risk for an allergic reaction that may result in hives, swelling, or anaphylaxis.
- To minimize the risk of an ocular injury, it is recommended that all clinicians be properly trained on how to use the SuperNO2VA™EtCO2 and be familiar with the Instructions For Use (IFU).
- To minimize the risk of a pressure, it is recommended that all clinicians be properly trained on how to use the SuperNO2VA™EtCO2, be familiar with the Instructions For Use (IFU), and monitor the subject's face for redness every 30 minutes that the SuperNO2VA™ EtCO2 is secured to the subject.

### 8.3. Potential Benefits to Subjects

- Improved oxygen delivery, administration, and oxygenation
- Potentially able to reduce post-op respiratory complications

### 8.4. Alternatives to Participation

The alternative for not participating in this study is not using the SuperNO2VA™ EtCO2 for gastrointestinal endoscopy.

## 9. CONFIDENTIALIATY OF DATA AND INFORMATION STORAGE

All study participants will be assigned a study number. The PI will maintain the key to the study number and medical record number in a password locked Indiana University computer. Information about study subjects will be kept confidential and managed according to the requirements of the Health Insurance Portability and Accountability Act of 1996 (HIPAA). Patient data will be entered into a password protected electronic spreadsheet and online database (i.e. REDCap). Only the investigators, who have been invited to participate in the study and who are registered with the IRB, as well as have documented completion of all IRB and HIPAA regulations will have access to patient data, but not the medical record key.

Electronic records will be stored for 5 years after study conclusion on the institution's password protected computer, after which time they will be deleted. If there is a breach in confidentiality or violation of IRB and HIPAA regulations, the IRB will be notified in a timely manner (within 7 days) and appropriate actions taken thereafter. All data used in the analysis and reporting of this investigation will be de-identified.

In order to ensure compliance with the Health Insurance Portability and Accountability Act (HIPAA), all subjects enrolled in the study will be required to provide authorization to disclose Protected Health Information (PHI). This authorization will be included in the informed consent document as required by the IRB. In all study reports and in any resulting publications, subjects will not be referred to by their initials and/or study identification number.

The co-PIs will monitor for safety. Data safety will be ensured by having all patient consents and information stored in the REDCaps system. After randomization patient and study data outside the REDCaps system will only be identified by study number. Any recruitment data and randomization tables will be stored as a single copy in a locked cabinet in a PI's secured Faculty office.

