## 4. SUBJECT IDENTIFICATION, RECRUITMENT AND CONSENT

### 4.1. Method Of Subject Identification And Recruitment

Subject consenting will take place at the GLES immediately prior to the procedure by key research personnel such as PI, Co-PIs, and/or study coordinators. Subject initials and/or study identification number will refer to the subjects.

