#### 4.2. Consent Process

Subjects deemed eligible to participate in the study will be explained in detail the purpose, nature and procedures of the study, as well as the potential risks, benefits and alternatives. They will be given a consent form to read and if they so choose, to discuss with friends, family, and other clinicians. They will be invited to ask questions and, after all questions are answered to their satisfaction, invited to sign the consent form. The Principal Investigator (with proper delegation of authority) will participate in the consenting process to ensure the subject has full understanding of the procedure and risks. No study-specific procedure will be performed before the consent form is signed.

Subject participation in this investigation is voluntary. Written informed consent is required from all subjects prior to the subject's participation in the investigation. Also, an obtained permission of the faculty anesthesiologist, in charge of the patient's anesthesia care, must also be granted for subject participation. If the subject is illiterate or unable to adequately read the informed consent form, a witness' signature and a cross mark or a fingerprint of the subject is required. In accordance with FDA regulation 21 CFR Part 50, informed Consent shall be obtained prior to any study procedure. The original of the signed consent will be retained at the investigational site. A signed copy of the consent will be given to the subject. While not anticipated, Sponsor will report any failure to obtain subject consent to the IRB within 5 days of learning of such an event, as required by regulation.

Prior to participating in this investigation, the site will be required to have an IRB-approved Informed Consent Document. Any modifications to the consent must be approved by Sponsor and by the IRB of record. The Principal Investigator at each study site is responsible for obtaining and maintaining the approved informed consent and forwarding an IRB-stamped copy to Sponsor.

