### 5.2 Methods:

This study involves the oxygenation, continuous positive airway pressure, and ventilation of a subject via nasal mask and oxygenation via a closed facemask. The interventions directly related to this study are that of supplement oxygen, bag-mask ventilation, and continuous nasal CPAP intra-operatively and in the Post Anesthesia Care Unit.

Patients will be randomized in groups of ten to one of two groups using a random number table. Group A: Standard care with a nasal cannula. Group B: SuperNO2VA™EtCO2.

For each anesthetic case, a preoperative history and physical and intraoperative record will be documented (table 1).

Table 1: General Patient characteristics	
Age (years)	
Gender (M/F)	
Height (cm)	
Weight (kg)	
BMI (kg/m  )	
ASA classification (I-III)	
Diagnosed OSA on home CPAP	
Diagnosed OSA not on home CPAP	
STOP-BANG Score	
Patient Co-morbidities*	

\*Co-morbidities include any history of: hypertension, diabetes, coronary disease, valvular disease, arrhythmia, cerebrovascular disease, active cancer, tobacco use, pulmonary disease, renal disease, liver disease.

Once in the endoscopy suite, the patients will have continuous monitoring of heart rate, end tidal CO2 (EtCO2), O2 saturation, and every 2-minute BP monitoring. Patients randomized to group A, the anesthesia provider will supply oxygen via nasal cannula at 10LPM. Patients randomized to group B, the anesthesia provider will attach the SuperNO2VAM EtCO2's circuit port to the hyperinflation bag with the oxygen flow rate to 10 L/min, and the APL valve completely closed. Initial dosing bolus 0.5-1.0 mg/kg actual body weight of Propofol will be administered for sedation and MOAA/S scores will be assessed. Nursing or the research assistant will then record the patient's MOAA/S score. If the patient's MOAA/S score of <4 reached. Once a MOAA/S score of <4 is reached the endoscopist will perform endoscopic intubation and the goal will be to maintain a MOAA/S score of <4 until the procedure is over. If the patient's MOAA/S score  $\geq 4$ , additional 10 – 40mg bolus of propofol will be administered every 30–90 seconds until the

Protocol #: IU IRB# 1810997768 Date: 31AUG21 Page 9 of 17

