### 10.2. Randomization

A random number generator program will be used to assign sequential qualified study cases to control group (N = 62) or SuperNO2VATMEtCO2 group (N = 62) before collection of additional demographic information and before anesthetic and surgical care. After study group assignment, baseline data will be collected, including age, gender, height, weight, and BMI.

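### The plan does not keep the randomisation list from the people who enrol patients, and its descriptions of the randomisation method need to be reconciled

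*Protocol*

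**What the plan says.** **Custody of the list.** Protocol section 9, on confidentiality and storage, states that "randomization tables will be stored as a single copy in a locked cabinet in a PI's secured Faculty office". It names no holder independent of recruitment.

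**Who enrols.** Section 4.1 has consent taken "immediately prior to the procedure by key research personnel such as PI, Co-PIs, and/or study coordinators". Section 4.2 adds: "The Principal Investigator (with proper delegation of authority) will participate in the consenting process". It also makes entry depend on a second clinician: "permission of the faculty anesthesiologist, in charge of the patient's anesthesia care, must also be granted for subject participation". When that permission is given relative to assignment is not stated.

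**Method.** Section 5.2 says: "Patients will be randomized in groups of ten to one of two groups using a random number table". Section 10.2, repeated in SAP 1.2, says: "A random number generator program will be used to assign sequential qualified study cases to control group (N = 62", with the same number for the mask group. Neither of those two places mentions groups of ten.

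**Order of steps.** Section 10.2 and SAP 1.2 place assignment before the collection of baseline data, and list height, weight and BMI among those data. Section 3.2 makes BMI of at least 35 kg/m², or documented sleep apnea, an entry criterion.

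**Visibility.** In one arm "the anesthesia provider will supply oxygen via nasal cannula at 10LPM"; in the other a nasal mask is attached to a hyperinflation bag. No masking is described.

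**Not described anywhere.** Sealed envelopes, central or REDCap release of the assignment, or a rule that all entry decisions are final before the arm is known.

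**The concern.** In an unmasked single-site trial, concealing the next assignment is the main protection against selection bias. Here the list sits with a member of the group that recruits. A lock keeps outsiders out but does not separate the custodian from enrolment. Even without sight of the list, staff can see every past assignment, and balanced groups let them infer something about the next one.

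Entry leaves room for discretion: whether to approach a patient that morning, whether the anesthesiologist agrees, and how a borderline BMI is judged. If someone expects the nasal cannula arm next, a patient who looks likely to desaturate can be entered; if the mask arm, the same patient can be passed over. That would move the desaturation rates directly, and both the intention-to-treat and the per-protocol comparison would inherit it.

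**Working it through.** **Step 1. The plan's 62:62 against groups of ten.** The total is 62 + 62 = 124, and 124 / 10 = 12.4, so the last group is incomplete. Suppose each ten holds five of each arm (inferred, not stated). Twelve full groups give 60:60, and four patients come from a thirteenth. The chance that these four split 2:2 is C(5,2) × C(5,2) / C(10,4) = 100 / 210 = 0.476. So balanced tens give 62:62 less than half the time, and the two descriptions are not one scheme in different words. Table versus generator could be reconciled by itself, since a program can print a table; the block structure and the fixed 62 per arm cannot.

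**Step 2. How guessable are balanced tens?** Assume that recruiters know the group size and see past assignments. With *a* and *b* places left in the group, the best guess is the arm with more places, correct with probability max(a, b) / (a + b). Averaged exactly over all orders, the values for positions 1 to 10 are 0.500, 0.556, 0.556, 0.595, 0.595, 0.643, 0.643, 0.722, 0.722 and 1.000. They sum to 6.53, or 65.3%. The next assignment is certain when one arm is used up. This happens for 1.67 of 10 patients (16.7%), or 12 × 1.67 = 20 patients over twelve groups.

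| Scheme | Best guess correct | Certain |
|---|---|---|
| Simple randomisation, list concealed | 50% | 0% |
| Single 62:62 list, no blocks | 55.2% | 1.6% |
| Balanced groups of ten | 65.3% | 16.7% |
| List seen | 100% | 100% |

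**Step 3. Effect on the test.** Assumptions: no device effect; event rate 28%, the mean of the plan's 43% and 13%; 62 per arm; two-sided 5% chi-square test. A recruiter who favours the mask enters a higher-risk patient when expecting cannula and a lower-risk one when expecting mask. If these two kinds of patient differ in risk by *d* and guesses are right with probability *A*, the spurious difference is D = (2A − 1) × d, and the arms run at 28% ± D/2. Exact enumeration of the two binomials gives:

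| Risk gap d | A | D | Cannula vs mask | False-positive rate |
|---|---|---|---|---|
| none | – | 0 | 28.0% vs 28.0% | 5.0% |
| 10 points | 0.653 | 3.1 points | 29.5% vs 26.5% | 6.6% |
| 20 points | 0.653 | 6.1 points | 31.1% vs 24.9% | 11.7% |
| 10 points | 1 | 10 points | 33% vs 23% | 23.6% |
| 20 points | 1 | 20 points | 38% vs 18% | 70.9% |

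The last two rows require every assignment to be seen and every place to be steered. They are upper bounds.

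**Step 4. Would changing the block sizes cure guessing?** A recruiter who does not know the sizes can still guess the arm used less so far. Simulated over 124 patients, this is right 65.0% of the time with fixed tens, 65.0% with a mix of 8, 10 and 12, and 68.0% with a mix of 4, 6 and 8. Known fixed blocks of 6 and 4 give 68.3% and 70.8%. Undisclosed mixing therefore reduces what is known with certainty but not best-guess accuracy, and smaller blocks raise it.

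**The case against.** **Section 9 is about storage.** It provides for a single locked copy. It does not say which PI holds the key or that this person enrols, and section 4.1 allows coordinators to take consent. This stands: a reader might infer that the list will be seen, and the documents do not show that. They show only that nothing prevents it.

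**The order of steps is partly given.** Section 10.2 assigns qualified cases in sequence, and written consent is an inclusion criterion, so consent and eligibility are implied to come first. This stands in part. The same section collects height, weight and BMI after assignment, and the anesthesiologist's permission has no stated place in the order.

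**The planned analysis can correct an imbalance.** A reader might conclude that no analysis could repair the bias; that is too strong. Section 10.3 and SAP 1.3 adjust when Table 1 factors differ significantly, and Table 1 records BMI, sleep apnea with and without home CPAP, and STOP-BANG. In a simulation of the 20-point guessing case, with steering on one recorded binary factor, the imbalance was flagged in about 95% of trials, and the adjust-if-different rule brought the false-positive rate from about 10–11% back to about 5%. The rule cannot reach bedside judgement that is not recorded.

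**Section 5.2 might mean ten consecutive patients to one arm.** That would make the next nine assignments known. The reading is strained, because 62 per arm is not a multiple of ten, and nothing here rests on it.

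**Conclusion.** The concern holds as a gap in design that should be closed. The list is held within the group that recruits, the treatments are visible, and no step conceals the next assignment. The method texts in section 5.2 and in section 10.2 with SAP 1.2 do not describe the same scheme, and BMI is collected after assignment although it determines entry.

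The size depends on assumptions that the documents do not settle: 5:5 balance within each ten, a group size known to recruiters, no masking (inferred from the devices and from silence on blinding), and a risk gap of 10 to 20 points that recruiters can recognise. Under these, guessing moves the false-positive rate from 5% to about 7–12%, before any adjustment for Table 1 factors. The 24–71% range should not be read as the expected error.

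**What to change.** Replace the method sentences in protocol sections 5.2 and 10.2 and in SAP 1.2 with one statement, for example:

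> The 1:1 allocation sequence, in permuted blocks of undisclosed varying size, will be computer-generated by a person who takes no part in recruitment and loaded into REDCap. The arm will be released only after consent, the anesthesiologist's permission, confirmed eligibility and baseline data, including height, weight and BMI, have been entered.

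- The person who prepares the list could be the trial statistician.
- Remove the paper randomisation table from section 9.
- Record the block sizes only in a document that enrolling staff cannot open. Keep them no smaller on average than ten, for example a mix of 8, 10 and 12.
- Do not present mixed blocks as a cure for guessing. The gain comes from independent custody and late release; mixing mainly removes assignments known with certainty.

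Section 9 already has the trial using REDCap, so the cost is a few hours of set-up and a wording amendment. The final split may differ from 62/62 by a few patients, with negligible effect on power.
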